6.3.2 Blinding

Not applicable.

6.4 Study Intervention Compliance

In this study, participants will receive study intervention at the study site. Well trained medical staff will monitor and perform the study intervention administration. The information of each study intervention administration, including the date, time, and dose of study intervention, will be recorded on the electronic case report forms (eCRFs). The Investigator will make sure that the information entered into the eCRF regarding study intervention administration is accurate for each participant. Any reason for noncompliance should be documented.

Noncompliance is defined as a participant missing > 1 infusion of study intervention for nonmedical reasons and barring any extenuating circumstances in the opinion of the Investigator. Extenuating circumstances should be documented and when possible, discussed with the Sponsor in advance. If 1 infusion is missed and the interval between the subsequent infusion and the last administered treatment is longer than 4 weeks for nonmedical reasons, the criterion of insufficient compliance is met as well.

Consequences of noncompliance may lead to discontinuation of study interventions as described in Section 7.1. In case of overdose, see Section 8.4.

6.5 Concomitant Therapy

Record in the eCRF all concomitant therapies (e.g., medicines or nondrug interventions) used from the time the participant signs the informed consent form until completion of the study, including any changes. For prescription and over-the-counter medicines, vaccines, vitamins, and herbal supplements, record the name, reason for use, dates administered, and dosing information.

Any additional concomitant therapy that becomes necessary during the study and any change to concomitant drugs must be recorded in the corresponding section of the eCRF, noting the name, dose, duration, and indication of each drug.

Contact the Medical Monitor for any questions on concomitant or prior therapy.

6.5.1 Permitted Medicines

The only permitted medications are the following:

1. Any medications (other than prohibited in Section 6.5.2) that are considered necessary for the participants' welfare and will not interfere with the study intervention may be given at the Investigator's discretion.
2. Other drugs to be used for non-steroid premedication (antihistamine and acetaminophen) for the treatment of anaphylactic reactions, IRRs, and severe hypersensitivity reactions/flu-like symptoms and irAEs (see Section 6.9).
3. Blood transfusions and erythroid growth factors are permitted as clinically indicated.

Any medicines that are considered necessary to protect the participant's welfare in emergencies may be given at the Investigator's discretion, regardless if it results in a protocol deviation.

6.5.2 Prohibited Medicines

The following treatments must not be administered during the 28-day Screening period and for the duration of study intervention. If the administration of a nonpermitted concomitant drug becomes necessary during the study, the participant will be withdrawn from study intervention (the Sponsor may be contacted to discuss whether the study intervention must be discontinued).

- Immunotherapy, immunosuppressive drugs (e.g., chemotherapy or systemic corticosteroids), or other experimental pharmaceutical products are prohibited. Exceptions are allowed for short-term treatment of allergic reactions or for the treatment of irAEs, specifically:
 - Short-term administration of systemic steroid (i.e., for allergic reactions or the management of irAEs) is allowed.
 - Steroids with no or minimal systemic effect (topical, intranasal, intro-ocular, inhalation) are allowed.
 - Hormone replacement with corticosteroids for adrenal insufficiency is allowed if the steroids are administered only for the purpose of hormonal replacement and at doses ≤ 10 mg or equivalent prednisone per day.
- Prophylactic use of corticosteroids for IRRs is prohibited.
- Concomitant local or regional treatment (radio/chemo-embolization) is prohibited.
- Other systemic anticancer therapy.
- Live vaccines are prohibited. Administration of inactivated vaccines is allowed (e.g., inactivated influenza vaccines).
- Any traditional Chinese medication used as anticancer treatment (regardless of the type of cancer) is prohibited. Traditional Chinese medication for indications other than anticancer treatment, such as supportive care, may be administered at the discretion of the Investigator. List of prohibited Chinese medications is provided in the [Appendix 7](#).
- Herbal remedies with immunostimulating properties (e.g., mistletoe extract) or known to potentially interfere with major organ function (e.g., hypericin).

Medications other than those specifically excluded in this study (see above) may be administered for the management of symptoms associated with the administration of bintrafusp alfa as required. These might include analgesics, anti-nausea medications, antihistamines, diuretics, antianxiety medications, and medication for pain management, including narcotic agents.

6.5.3 Other Interventions

Permitted Procedures

- Palliative organ-sparing radiotherapy may be administered only for specific clinical indications during the study. The assessment of PD will be made according to RECIST 1.1 and not based on the necessity for palliative radiotherapy.

Prohibited Procedures

- Major surgery within 4 weeks before the start of the study. Discuss with the Medical Monitor if unplanned major surgery is required on study to plan for timing of re-treatment. Any diagnostic biopsies collected for clinical reasons during the study should be documented as a concomitant procedure including the outcome of available pathology reports.

6.6 Dose Selection and Modification

Participants will receive an IV infusion of bintrafusp alfa at a dose of 1200 mg over 1 hour CCI [REDACTED] once every 2 weeks as detailed in the SoA (see [Table 1](#)).

Dose modification of bintrafusp alfa is not allowed.

6.7 Study Intervention after the End of the Study

After a participant has completed the study, has withdrawn consent, or has been withdrawn early, symptom guided appropriate treatment will be administered, if required, in accordance with the study site's standard of care and generally accepted medical practice and depending on the participant's individual medical needs.

On withdrawal from the study, participants may receive whatever care they and their physicians agree upon.

6.8 Special Precautions

Any treatment-emergent adverse event (TEAE) that is assessed as potentially related to bintrafusp alfa, may require permanent or transient discontinuation of bintrafusp alfa treatment.

Single laboratory values out of the normal range that do not have any clinical correlation do not necessarily need treatment interruption. Questions or concerns with regard to management and/or follow-up of TEAEs should be discussed with the Medical Monitor.

Immune-related AEs, IRRs including hypersensitivity, anemia, TGF- β inhibition mediated skin reactions, and bleeding events are managed and followed up in their respective sections as indicated below. Permanent study intervention discontinuation may be recommended, so the relevant section must be reviewed:

- For suspected irAEs, general management by NCI-CTCAE v5.0 toxicity grading is listed in Section 6.9.2. Recommended guidance and management for specific irAEs as per published guidelines is provided in [Appendix 5](#).
- Infusion-related reaction (IRR) and hypersensitivity reaction guidance are presented in Section 6.9.1.
- Anemia guidance is presented in Section 6.9.4.
- Potential TGF- β -mediated skin AEs guidance and management are provided in Section 6.9.3.
- For guidance and management of bleeding events, see Section 6.9.5.

General guidance:

- In any case, if ≥ 2 doses are missed due to AE, the Medical Monitor should be consulted
- Inability to reduce corticosteroid dose to 10 mg or less of prednisone or equivalent per day within 12 weeks is an indication for permanent treatment discontinuation (except for use of steroids as hormone substitution)
- Persistent Grade 2 or 3 adverse reactions (excluding endocrinopathies controlled with hormone replacement therapy) that do not recover to Grade 0 to 1 within 12 weeks after last dose of study intervention is an indication for permanent treatment discontinuation.

In general, the following applies for TEAEs related to bintrafusp alfa that are not covered by the recommendations for irAE management in [Appendix 5](#):

Grade 4 treatment-related TEAEs

Any Grade 4 treatment-related TEAEs require permanent treatment discontinuation, except:

- Endocrinopathies that have been controlled by hormone replacement
- Isolated laboratory values out of normal range that do not have any clinical correlation. Discuss with Medical Monitor regarding work-up, management, and treatment continuation versus hold versus discontinuation for isolated Grade 4 laboratory abnormalities
- If alternative explanation is identified for Grade 4 non-tumor bleeding.

See [Appendix 5](#) for guidance on specific Grade 4 irAEs, as most require permanent treatment discontinuation.

Grade 3 treatment-related TEAE

1. Participants with any severe or Grade 3 treatment-related adverse reactions that recur should be permanently discontinued. Exceptions may be considered for the following after discussion with Medical Monitor:
 - Transient Grade 3 flu-like symptoms or fever that is controlled with medical management

- Transient Grade 3 fatigue, local reactions, headache, nausea, emesis that resolves to \leq Grade 1 or baseline
 - Tumor flare phenomenon defined as local pain, irritation, or rash localized at sites of known or suspected tumors
 - Any Grade \geq 3 drug-related amylase or lipase abnormality that is not associated with symptoms or clinical manifestations of pancreatitis
 - Grade 3 Hgb decrease (< 8.0 g/dL) that is clinically manageable with blood transfusions or erythroid growth factor use
 - Increases in ECOG PS \geq 3 that resolves to \leq 2 by Day 1 of the next infusion (i.e., infusions should not be given if the ECOG PS is \geq 3 on the day of treatment and should be delayed until ECOG PS \leq 2)
 - Keratoacanthoma (KA) and cutaneous squamous cell carcinoma (cSCC)
 - Grade 3 non-tumor bleeding requiring intervention or hospitalization if alternative explanation can be identified (such as concomitant use of antithrombotic agents, traumatic event, etc.).
2. See [Appendix 5](#) for guidance on specific Grade 3 irAEs as many require permanent treatment discontinuation, including pneumonitis and nephritis.
 - AST or ALT $>$ 5 times ULN or total bilirubin greater than 3 times ULN must be permanently discontinued, except for participants with liver metastases (for example) who begin treatment with Grade 2 AST or ALT. These participants should be discontinued if AST or ALT increases by \geq 50% relative to baseline and lasts for at least 1 week.
 3. Persistent Grade 3 adverse reactions (excluding endocrinopathies controlled with hormone replacement therapy) that do not recover to Grade 0 to 1 within 12 weeks after dose of treatment.

Grade 2 treatment-related TEAE

1. If a Grade 2 treatment-related TEAE resolves to Grade \leq 1 by the day before the next infusion, study intervention may be continued.
2. If a Grade 2 treatment-related TEAE does not resolve to Grade \leq 1 by the day before the next infusion, but it is manageable and/or not clinically relevant, the Medical Monitor should be consulted to assess if it is clinically reasonable to administer the following infusion.

Note that treatment recommendations regarding continuation, hold, or discontinuation by grade are different depending on the specific toxicity (refer to [Appendix 5](#)). Toxicity grading is assigned based on NCI-CTCAE v5.0.

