 - a. Adequate hematological function defined by absolute neutrophil count (ANC) $\geq 1.5 \times 10^9/L$, platelet count $\geq 100 \times 10^9/L$, and hemoglobin (Hgb) ≥ 9 g/dL.

- b. Adequate hepatic function defined by a total bilirubin level \leq the upper limit of normal (ULN), aspartate aminotransferase (AST) and alanine aminotransferase (ALT) levels $\leq 1.5 \times$ ULN. For participants with liver involvement in their tumor, AST $\leq 5.0 \times$ ULN, ALT $\leq 5.0 \times$ ULN, and bilirubin $\leq 3.0 \times$ ULN are acceptable.
 - c. Adequate renal function defined by creatinine $\leq 1.5 \times$ ULN or calculated creatinine clearance (CrCL) ≥ 30 mL/min for participant with creatinine $> 1.5 \times$ ULN (glomerular filtration rate can also be used).
 - Note: CrCL should be calculated per institutional standard. If no local guideline is available, CrCL should be calculated using the Cockcroft-Gault Method:
$$\text{CrCL} = ([140 - \text{age}] \times \text{weight [kg]} \times [0.85 \text{ for females only}]) / (72 \times \text{creatinine}).$$
 - d. Adequate coagulation function defined as international normalized ratio (INR) or prothrombin time (PT) $\leq 1.5 \times$ ULN unless the participant is receiving anticoagulant therapy and activated partial thromboplastin time (aPTT) $\leq 1.5 \times$ ULN unless the participant is receiving anticoagulant therapy.
8. Participants with known HIV infections are in general eligible if the following criteria are met ([FDA Guidance on Cancer Clinical Trial Eligibility, March 2019](#)):
- a. If clinically indicated patients must be stable on antiretroviral therapy (ART) for at least 4 weeks and agree to adhere to ART. If not clinically indicated, consult study Medical Monitor.
 - b. Participants with HIV infection should have no evidence of documented multi-drug resistance that would prevent effective ART.
 - c. Have an HIV viral load of < 400 copies/mL at Screening.
 - d. Have CD4+ T-cell (CD4+) counts ≥ 350 cells/ μ L.
 - e. For patients with a history of an AIDS-defining opportunistic infection within the last 12 months, patients may be eligible only after consultation and agreement with the study Medical Monitor.
 - f. If prophylactic antimicrobial drugs are indicated, patient may still be considered eligible upon agreement with the study Medical Monitor.

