G2: Asymptomatic (AST or ALT > 3.0 to ≤ 5 x ULN and/or total bilirubin > 1.5 to ≤ 3 x ULN)	
Hold ICPI temporarily and resume if recover to G1 or less on prednisone ≤ 10 mg/d
 
For Grade 2 hepatic toxicity with symptoms, may administer corticosteroid 0.5-1 mg/kg/d prednisone or equivalent if the abnormal elevation persists with significant clinical symptoms in 3-5 days Increase frequency of monitoring to every 3 days
 
Infliximab might not be the most appropriate treatment option in the situation of immune-mediated hepatitis given the potential risk of idiosyncratic liver failure (Note: No clear evidence shows the liver toxicity from infliximab from other studies)
 
In follow-up, may resume ICPI treatment followed by taper only when symptoms improve to G1 or less and corticosteroid ≤ 10 mg/d; taper over at least 1 month
 
Patients should be advised to stop unnecessary medications and any known hepatotoxic drugs

G3: Symptomatic liver dysfunction, fibrosis by biopsy, compensated cirrhosis, reactivation of chronic hepatitis (AST or ALT 5-20 x ULN and/or total bilirubin 3-10x3 ULN)	
Permanently discontinue ICPI
 
Immediately start corticosteroid 1-2 mg/kg methylprednisolone or equivalent
 
If corticosteroid refractory or no improvement after 3 days, consider mycophenolate mofetil or azathioprine (if using azathioprine should test for thiopurine methyltransferase deficiency)
 
Laboratories at daily or every other day; consider inpatient monitoring for patients with AST/ALT > 8 x ULN and/or elevated TB 3 x ULN
 
Increase frequency of monitoring to every 1-2 days

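### For participants with liver metastases who start with Grade 2 AST or ALT, Protocol 6.8 and the hepatitis table in Appendix 5 give contradictory stop and hold instructions at the same laboratory value

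*Protocol*

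**What the plan says.** Three parts of the protocol bear on the same participants.

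- **Section 5.1, criterion 7b.** The usual entry limits are AST and ALT up to 1.5 x ULN and bilirubin up to ULN. "For participants with liver involvement in their tumor", the limits are 5.0 x ULN for AST and ALT and 3.0 x ULN for bilirubin.
- **Section 6.8, Grade 3 events, item 2, liver bullet.** AST or ALT above 5 x ULN is a permanent stop, and the same sentence goes on to bilirubin and to an exception: "total bilirubin greater than 3 times ULN must be permanently discontinued, except for participants with liver metastases (for example) who begin treatment". The exempt group is limited to those whose AST or ALT is Grade 2 at that point. For the exempt group: "These participants should be discontinued if AST or ALT increases by" at least "50% relative to baseline and lasts for at least 1 week".
- **Appendix 5, Table A2, 2.2 Hepatitis.** Grade 1 (AST or ALT up to 3.0 x ULN) continues. Grade 2 (> 3.0 to 5 x ULN) holds treatment "temporarily and resume if recover to G1 or less on prednisone" of at most 10 mg/day. Grade 3, which includes "reactivation of chronic hepatitis (AST or ALT 5-20 x ULN and/or total bilirubin 3-10x3 ULN", is permanent discontinuation, and so is Grade 4. No row refers to a baseline value.

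Section 6.8 also has a scope sentence ahead of its graded rules, limiting them to related TEAEs that Appendix 5 does not cover. The liver bullet, however, is nested under the item that sends sites to Appendix 5 for Grade 3 immune-related events.

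**The concern.** Criterion 7b deliberately admits people with raised transaminases, and 6.8 deliberately gives them a rule tied to their own baseline. Table A2 does not carry that rule. A site faced with a raised transaminase is pointed to both places and can find a permanent stop in one and no stop in the other.

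These are mandatory-sounding instructions on stopping treatment. If sites resolve the conflict differently, identical laboratory values will end treatment at one site and not at another. That bears on participant safety and exposure, and on the meaning of the planned tables of TEAEs leading to permanent discontinuation (SAP 15.1.2).

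**Working it through.** The plan gives no figure to reproduce; the check is a comparison of thresholds.

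**Inputs.** Let b be the baseline and x the on-study AST or ALT, both in multiples of ULN.

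- 6.8, ordinary rule: stop if x > 5.
- 6.8, exempt group: discontinue if x ≥ 1.5b for at least 1 week.
- Table A2: hold if 3 < x ≤ 5; stop permanently if x > 5. (The printed bands both contain exactly 5; it is treated here as Grade 2.)
- Assumption: Grade 2 at entry means 3 < b ≤ 5. Section 6.8 grades by NCI-CTCAE v5.0, whose cut-offs the protocol does not print, so Table A2's band is used.

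**Thresholds.** The 6.8 threshold runs from just above 1.5 × 3.0 = 4.5 to 1.5 × 5.0 = 7.5. It equals Table A2's 5 only when b = 5 / 1.5 = 3.33.

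- For b > 3.33, values with 5 < x < 1.5b are a permanent stop in Table A2 but do not meet the 6.8 stop. The width is 1.5b − 5: 1.0 at b = 4.0, 1.75 at b = 4.5, and 2.5 at b = 5.0, the maximum.
- For 3 < b < 3.33, values with 1.5b ≤ x ≤ 5 lasting a week are a discontinuation in 6.8 but a hold in Table A2. The width is 5 − 1.5b: 0.35 at b = 3.1, and always below 0.5.

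| b | x | Rise | 1.5b | 6.8 | Table A2 |
|---|---|---|---|---|---|
| 4.5 | 6.0 | 6.0/4.5 = 1.33, +33% | 6.75 | stop not met | permanent stop |
| 4.0 | 5.5 | 5.5/4.0 = 1.375, +37.5% | 6.0 | stop not met | permanent stop |
| 5.0 | 7.4 | 7.4/5.0 = 1.48, +48% | 7.5 | stop not met | permanent stop |
| 3.1 | 4.7 (1 week) | 4.7/3.1 = 1.516, +52% | 4.65 | discontinue | hold, may resume |
| 2.0 | 5.5 | not exempt | – | permanent stop | permanent stop |

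The last row shows the boundary of the problem: at baselines of 3 x ULN or below, both texts stop above 5.

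**Recovery.** Table A2 ties resumption to Grade 1 or less, that is x ≤ 3. After an on-study event, someone who entered at 4.0 must fall to (4.0 − 3.0)/4.0 = 25% below her own entry value; at 5.0 the figure is 40%. Section 6.8 separately makes failure to recover to Grade 0-1 within 12 weeks of the last dose an indication for permanent discontinuation.

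**Bilirubin.** The exception clause in 6.8 follows both the AST/ALT limit and the bilirubin > 3 x ULN limit, so read literally it lifts both. The replacement rule names only AST and ALT. The text therefore leaves no stated bilirubin stop in 6.8 for the exempt group.

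**The case against.** The strongest reply is the scope sentence in 6.8. On a strict reading, immune-related hepatitis follows Table A2, other related liver events follow 6.8, and the two never meet. Section 6.8 also says that recommendations differ by toxicity.

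This narrows the conflict but does not remove it. The liver bullet sits under the immune-related item, not among the rules for other events. Table A2 starts the work-up for other causes, including liver metastasis, at Grade 2, so the hold-or-stop decision arises while the cause is still open. Its printed definition of hepatitis refers to a viral process and cannot sort the cases. Nothing says which text governs a raised transaminase of undetermined cause.

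Several stronger readings are tempting, and the documents do not support them:

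- **That 6.8 contradicts eligibility.** The entry maxima (5.0 and 3.0 x ULN) do not exceed the 6.8 limits (> 5 and > 3), and the exception accommodates raised baselines. It is Table A2 that makes no allowance for what criterion 7b admits.
- **That everyone with liver involvement is affected.** Only those entering above 3 x ULN are.
- **That a participant entering at 4 x ULN must be held on Day 1.** Appendix 4 treats conditions present at the first visit that do not worsen as baseline conditions, not AEs. The recovery difficulty arises only after an on-study event.
- **That any bilirubin rise from 3.0 x ULN forces a permanent stop.** For the exempt group the text is a gap. The ordinary limit still applies to participants outside the exception, for treatment-related events.
- **That 6.8 authorizes dosing between 5 and 7.5 x ULN.** Not meeting a stop is not permission to dose; 6.9.2 generally suspends treatment for Grade 3 immune-related events.

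**Conclusion.** The contradiction stands for one defined group: participants with liver metastases who begin treatment with Grade 2 AST or ALT. The same value can give opposite instructions in both directions, over a band of up to 2.5 x ULN in one direction and less than 0.5 x ULN in the other. In the second direction the contrast is between a discontinuation and a hold; the exception sentence in 6.8 does not itself use the word permanent.

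Every 1.5b figure depends on taking Grade 2 as > 3 to 5 x ULN. The documents give no count of participants in this group, so the effect on exposure or on discontinuation rates cannot be sized. A reader might infer that the primary result is at risk; nothing here changes the sample size, power or ORR analysis, and any effect on response is conjecture. The point merits correction because it concerns patient safety and consistent conduct across sites.

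**What to change.** Reconcile criterion 7b in 5.1, the scope sentence and liver bullet in 6.8, and the hepatitis rows of Table A2, so that participants entering with raised AST or ALT have one consistent instruction. In both 6.8 and Table A2, state:

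- which text governs, including while the cause of a rise is undetermined;
- whether the baseline-referenced rule replaces the ULN-referenced rows for this group, and what recovery means for someone who entered above 3 x ULN;
- whether that rule covers bilirubin;
- the AST and ALT range meant by Grade 2 at entry.

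Which limits apply is a decision for the sponsor's medical lead, and none is proposed here. The cost is wording in two places, with the usual review of a protocol change, and a letter to sites. AST, ALT and bilirubin are already collected at screening and on study, so no new data are needed.
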